2.7.4.2 Vital signs

Measurements of vital signs and body weight done more than 30 days after discontinuation of study medication will be excluded from the analysis.

The change from baseline in diastolic blood pressure, systolic blood pressure, pulse rate, and weight will be summarized by scheduled visit with n, mean, SD, minimum, median, and maximum values. Furthermore, the number (%) of patients with notably abnormal vital signs or weight will be presented by visit and for time point 'at any time after baseline'.

The criteria for notably abnormal vital signs and weight are displayed in [Table 2-2](#).

Table 2-2 Definition of notable ranges for vital signs and weight

Parameter	Criteria for notable ranges
Systolic blood pressure	≥ 180 mmHg / ≤ 90 mmHg with increase / decrease from baseline of ≥ 20 mmHg
Diastolic blood pressure	≥ 105 mmHg / ≤ 50 mmHg with increase / decrease from baseline of ≥ 15 mmHg
Pulse rate	≥ 120 bpm / ≤ 50 bpm with increase / decrease from baseline of ≥ 15 bpm
Weight	$\geq 7\%$ increase or decrease from baseline weight

The vital sign data of patients with notably abnormal vital signs will be listed. Similarly body weight data of patients with notably abnormal body weight will be listed.

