5.2 Inclusion criteria

Patients eligible for inclusion in this study must meet **all** of the following criteria:

- Male or female aged ≥ 10 years with non-transfusion-dependent congenital or chronic anemias inclusive of beta-thalassemia intermedia, HbE beta-thalassemia or alpha-thalassemia intermedia (HbH disease)
- LIC ≥ 5 mg Fe/g dw measured by R2 MRI at screening
- Serum ferritin ≥ 300 ng/mL at screening (two consecutive values at least 14 days apart from each other)
- Written informed consent obtained prior to any screening procedures

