5.4 Exclusion criteria for pediatric patients

- A patient's weight of at least 20 kg is required to allow dosing of 5 mg/kg with one tablet of 125 mg

6 Treatment

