6.5 Treatment duration

The duration of treatment will be five years.

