7.2.2.3 Height and weight

All subjects will have standing height measured at Screening Visit 1 or Visit 2. Pediatric patients will also have their height measured at Visits 15, 25, 34, 44, 53, 63, 72, 82, 91, and End of Treatment. Adult patients will have height measured yearly (Visits 25, 44, 63, 82 and

End of Treatment). Height will be measured in centimeters. This height measurement must be captured in the eCRF.

Body weight will be recorded for all patients at screening (Visit 1 or Visit 2), then at 4 week intervals and captured on the eCRF. Body weight will be measured to the nearest 0.1 kilogram. Weight must be measured while the patient is wearing ordinary clothing without shoes.

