Cmax	Maximum (peak) observed plasma concentration after single dose administration
CSR	Clinical Study report
CTCAE	Common Terminology Criteria for Adverse Events
DMC	Data Monitoring Committee
dw	Dry weight
ECG	Electrocardiogram
eCRF	Electronic Case Report/Record Form
EOS	End of study
FAS	Full Analysis Set
FE	Iron
FSH	Follicle stimulating hormone
GGT	Gamma glutamyl transferase
HbE	Hemoglobin E
HbH	Hemoglobin H
LDH	lactase dehydrogenase
LH	Luteinizing hormone
LIC	Liver iron content
LPLV	Last patient last visit
MedDRA	Medical Dictionary for Drug Regulatory Affairs
MRI	Magnetic resonance imaging
NTDT	Non-transfusion-dependent thalassemia
o.d.	Once Daily
OS	Overall Survival
PedsQL™	Pediatric Quality of Life Inventory™
PFS	Progression-Free Survival
PK	Pharmacokinetics
PPS	Per-Protocol Set
PRO	Patient-reported Outcomes
qd	Qua'que di'e / once a day
QoL	Quality of Life
RAP	Report and Analysis Process
RECIST	Response Evaluation Criteria in Solid Tumors
SAE	Serious adverse event

SAP	Statistical Analysis Plan
SD	Standard deviation
SF	Serum ferritin
SF-36	Medical Outcomes study short form-36
SF-6D	Short-Form Six-Dimension
SOC	System Organ Class
THALASSA	Novartis Study CICL670E2209
TFLs	Tables, Figures, Listings
Tmax	Time to reach maximum (peak) plasma concentration after single dose administration
TSH	Thyroid stimulating hormone
WHO	World Health Organization

1 Introduction

CICL670E2419 is a phase IV open label, multi-center, efficacy and safety study of deferasirox in iron overloaded patients with non-transfusion dependent thalassemia. This open-label, single-arm, multi-center 5-year study was designed to evaluate the efficacy and safety of deferasirox in iron overloaded NTDT patients, at least ten-years-old. A 1-year analysis was performed to assess the primary objective and selected secondary objectives. This study enrolled 134 patients including 68 Chinese and 66 non-Chinese, with 112 patients still on treatment at the time of the 1-year primary analysis.

The primary objective of this one-year analysis was met, confirming activity of deferasirox in the NTDT population, as observed in Study ICL670A2209. The absolute change in LIC from Baseline to Week 52 was statistically significantly different (Paired T-test, $p<0.0001$, two-sided). The absolute mean change in LIC (mg Fe/g dw) from Baseline to Week 52 was -6.68 (SD 7.018) with a 95% CI (-7.91, -5.45).

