For all variables, the baseline value will be defined to be the last available value prior to or on Day 1.

For serum ferritin the baseline value will be calculated from the mean of values measured prior to or on Day 1.

Last assessment day

For the safety assessment, the censoring date will be the last treatment date+30 days. For example, time to first specific adverse event will be censored at the last treatment date+30 days for a patient without the specified adverse event on-treatment.

End of treatment year 1

All data collected at Week 52 visit will be noted as End of treatment year 1

Month definition

Unless otherwise noted (e.g. for the calculation for month of exposure, 1 month = 365.25/12 days), one month will be defined as 30 days, with the exception of month 1 which consisted the first 45 days. When multiple values will be present for a month, the average value will be used unless otherwise noted. The grouping of each month will be according to the following rules:

- If the day is in (1, 30+15] assign to month 1.
- If the day is in (30*x-15, 30*x+15] assign to month x<12.
- If the day is in (345, 378] assign to month 12.

This would allow for a +/- 15 days window for each month.

Quarter definition

Unless otherwise noted, the quarter is defined as shown in the table below:

Visit Description	First day in window	Scheduled day in window	Last day in window	Quarter
Baseline	-35		1	
Week 2	2	14	21	1
Week 4	22	28	42	1
Week 8	43	56	70	1
Week 12	71	84	98	1
Week 16	99	112	126	2
Week 20	127	140	154	2
Week 24	155	168	182	2
Week 28	183	196	210	3
Week 32	211	224	238	3
Week 36	239	252	266	3
Week 40	267	280	294	4

Visit Description	First day in window	Scheduled day in window	Last day in window	Quarter
Week 44	295	308	322	4
Week 48	323	336	350	4
Week 52	351	364	378	4
Week 56	379	392	406	5
Week 60	407	420	434	5
Week 64	435	448	462	5
Week 68	463	476	490	6
Week 72	491	504	518	6
Week 76	519	532	546	6
Week 80	547	560	574	7
Week 84	575	588	602	7
Week 88	603	616	630	7
Week 92	631	644	658	8
Week 96	659	672	686	8
Week 100	687	700	714	8
Week 104	715	728	742	8
Week 108	743	756	770	9
Week 112	771	784	798	9
Week 116	799	812	826	9
Week 120	827	840	854	10
Week 124	855	868	882	10
Week 128	883	896	910	10
Week 132	911	924	938	11
Week 136	939	952	966	11
Week 140	967	980	994	11
Week 144	995	1008	1022	12
Week 148	1023	1036	1050	12
Week 152	1051	1064	1078	12
Week 156	1079	1092	1106	12

Visit Description	First day in window	Scheduled day in window	Last day in window	Quarter

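### The SAP's 7% notable-weight rule has no age limit, so in patients who enter as children it mixes normal growth with abnormality and does not pick up flat weight

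*SAP*

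**What the plan says.** **The rule.** SAP 2.7.4.2, Table 2-2, sets one weight criterion: 7% or more "increase or decrease from baseline weight". It has no qualifier for age, height or expected growth. The same section says that "the number (%) of patients with notably abnormal vital signs or weight will be presented by visit", and also over the whole post-baseline period. Weights of flagged patients are listed. Nothing requires increases and decreases to be counted separately.

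**The reference value.** SAP 2.1.1: "For all variables, the baseline value will be defined to be the last available value prior to or on Day 1". The comparison weight is never updated.

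**The population and duration.** Protocol 5.2 admits "Male or female aged ≥ 10 years", and the SAP introduction describes the study as one "in iron overloaded NTDT patients, at least ten-years-old". Protocol 5.4 adds for children: "A patient's weight of at least 20 kg is required". Protocol 6.5: "The duration of treatment will be five years". Weight is taken at 4-week intervals (Protocol 7.2.2.3).

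**Height.** Protocol 7.2.2.3: "Pediatric patients will also have their height measured at Visits 15, 25, 34", with further visits about every six months up to End of Treatment. In the SAP, height appears only in the Schwartz creatinine clearance formula (SAP 5.2). It is absent from the baseline characteristics (SAP 2.3) and from the other safety data (SAP 2.7.4).

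**Age groups.** SAP 2.2.1 defines subgroups below 18 and from 18 years. SAP 2.4.1 promises summaries by age for selected efficacy and safety parameters, without naming weight. SAP 2.1 makes ethnicity group and all patients the default layout.

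**The concern.** A fixed percentage change from baseline is a reasonable screen in adults, whose expected change is near zero. In a growing child the expected change is positive and accumulates over time, so the same screen reads growth as an abnormality. It also reads an absence of growth as no change, and so as normal.

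What is at stake is how the notable-weight table reads in a five-year safety report. A high count of flagged patients could reflect adult weight change, childhood growth or both, and the planned table would not separate them. The signal that matters most in a child, weight or height falling behind age, has no planned display, although both measurements are collected. The protocol names endocrine dysfunction as a complication of iron overload (Protocol 1.1) and makes endocrine function a secondary objective (Protocol 3), so growth is relevant context.

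**Working it through.** The 7% threshold is a set rule and not a derived figure, so there is no plan figure to reproduce. The check is how much growth reaches it.

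**Inputs from the documents.** Threshold 7% of baseline weight (SAP Table 2-2); fixed baseline (SAP 2.1.1); entry from age 10 (Protocol 5.2) and, for children, from 20 kg (Protocol 5.4); five years of treatment (Protocol 6.5).

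**Assumptions.** The documents give neither growth rates nor the weights of enrolled children. I take a steady gain g of 1 to 5 kg a year and starting weights W from 20 to 55 kg.

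**Annual rate that reaches the threshold at year 5.** Compounded: 1.07^(1/5) − 1 = 1.36% a year. Linear: 7% / 5 = 1.4% a year.

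**By starting weight.** Gain needed = 0.07 × W. Yearly gain that just reaches it at year 5 = 0.07 × W / 5. Time to flag = 0.07 × W / g. Change at year 5 = 100 × 5g / W.

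| W (kg) | Gain needed (kg) | Yearly gain reaching it at year 5 (kg) | Years to flag, g = 1 | Years to flag, g = 5 | Change at year 5, g = 1 |
|---|---|---|---|---|---|
| 20 | 1.40 | 0.28 | 1.40 | 0.28 | +25.0% |
| 30 | 2.10 | 0.42 | 2.10 | 0.42 | +16.7% |
| 40 | 2.80 | 0.56 | 2.80 | 0.56 | +12.5% |
| 50 | 3.50 | 0.70 | 3.50 | 0.70 | +10.0% |
| 55 | 3.85 | 0.77 | 3.85 | 0.77 | +9.1% |

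Every combination in this range passes +7% within five years. The slowest is 55 kg at 1 kg a year, at 3.85 years.

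**The opposite case.** A child whose weight is the same at year 5 as on Day 1 has a change of 0% and is not flagged. Nor is any change strictly between −7% and +7%.

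**Where the flag need not occur.** A patient near the end of growth may gain less than the yearly gain in the third column. At 1% a year compounded, the five-year gain is 1.01^5 − 1 = 5.1%, below the threshold. A child who leaves before the crossing time is not flagged either, because SAP 2.7.4.2 drops weights taken more than 30 days after discontinuation.

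**The case against.** The strongest reply is that this is a descriptive screening count in a single-arm study. It enters no hypothesis test, and growth is not a listed objective or endpoint. That stands, and it limits the importance of the point.

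Three stronger readings are tempting, and the documents do not support them.

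- A reader might infer that failure to grow can never be seen. A loss of 7% or more is flagged, and significant findings after the start of study are recorded as adverse events (SAP 2.7.4). The supported claim is that flat weight meets no notable-range criterion. The adverse-event route depends on the investigator's judgement and does not correct the table.
- A reader might infer that the trial's growth data go unanalysed. Weight is itself growth data, and its change from baseline is summarised by visit. Only height has no summary.
- A reader might want to size the distortion. If 10% to 20% of patients were under 18 and every one were flagged through growth alone, the rate over the whole post-baseline period would include 10 to 20 percentage points of growth. That is a ceiling resting on an under-18 share that the documents do not give. Some older adolescents would not cross, some patients would be flagged for other reasons, and follow-up is incomplete: the SAP introduction reports 112 of 134 patients still on treatment at the one-year analysis.

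The promised summaries by age are a partial answer. Weight may be among the selected parameters, but the SAP does not say so, and the same criterion would still apply within the younger group.

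**Conclusion.** The point holds in a limited form. As written, Table 2-2 counts ordinary growth as notably abnormal and leaves flat weight in a growing child unflagged, and no other section of the SAP changes that rule. The crossing times rest on the assumed steady gains of 1 to 5 kg a year and starting weights of 20 to 55 kg. The general conclusion needs only a sustained gain of about 1.4% a year over five years.

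The effect on the reported percentage cannot be sized, because neither the number of patients under 18 nor their growth rates are in the documents. The consequence is confined to the interpretation of one descriptive safety table. The primary endpoint is unaffected.

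**What to change.** In SAP 2.7.4.2 and Table 2-2:

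- Apply the 7% increase criterion only to patients aged 18 or over at baseline. Keep the decrease criterion for all patients.
- Report increases and decreases in separate rows.
- Show weight change and notable weight by the age groups already defined in SAP 2.2.1.
- For patients under 18 at baseline, summarise change in age- and sex-standardised weight and height, or growth velocity, at the scheduled height visits. This is needed because a flag for decreases alone would still miss stalled growth and would drop any view of excess gain; the standardised summary shows both.

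The cost is SAP wording and one extra table from data already collected. The SAP must also name a growth reference suited to a multi-country population (68 Chinese and 66 non-Chinese patients). It should say how patients are handled once they are older than that reference covers: a patient who enters at 17 is 22 after five years. With few children, the table will be descriptive only. On an assumed 10% to 20% share of 134 patients, it would hold about 13 to 27 (0.10 × 134 = 13.4; 0.20 × 134 = 26.8).

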2.7.4.3 Tolerability

The following GI events (grouped) will be analyzed:

- Abdominal pain/ GI pain (preferred terms of Abdominal discomfort, Abdominal pain, Abdominal pain lower, Abdominal pain upper, Abdominal tenderness, Epigastric discomfort, or Gastrointestinal pain)
- Dyspepsia (preferred terms of Dyspepsia)
- Diarrhoea (preferred terms of Diarrhoea, Diarrhoea neonatal, or Frequent bowel movements)
- Constipation (preferred terms of Constipation, Faeces hard, or Infrequent bowel movements)
- Vomiting (preferred terms of Discoloured vomit, Nausea, Retching, or Vomiting)
- Abdominal distension (preferred terms of Abdominal distension)
- Oesophagitis (preferred terms of Oesophageal discomfort, Oesophageal irritation, Oesophageal mucosa erythema, Oesophageal pain, or Oesophagitis)

These events will be investigated with regards to frequency, time to onset, duration and outcome (event end yes/no). For each patient and type of event the following will be determined:

- Number of events
- Time to first event
- Duration of first event

All variables of type 'number of events' will be summarized in frequency tables showing the number and percentage of patients with 0, 1, 2, ≥ 3 events, and with descriptive statistics (n, mean, SD, minimum, median, maximum, sum). The median time to first event and the median duration of first event will be estimated using Kaplan-Meier methods. The analysis of the duration of first event only included patients with event. In the analysis of time to first event,

patients without event will be considered censored at their last assessment date. In the analysis of duration of first event, patients without end of event will be considered censored at their last assessment date. Incidences of grouped gastro-intestinal adverse events will be presented.

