Deferasirox has demonstrated acceptable safety and tolerability in adult and pediatric patients with transfusional iron overload (Piga 2005, Cappellini 2006, Vichinsky 2007). The most frequent reactions reported during chronic treatment with deferasirox in adult and pediatric patients included gastrointestinal disturbances in about 26% of patients (mainly nausea, vomiting, diarrhea, or abdominal pain), and skin rash in approximately 7% of patients. These reactions were dose-dependent, mostly mild to moderate, generally transient and most resolved even if treatment was continued. In addition, there have been rare reports of upper gastrointestinal hemorrhages and ulcerations, primarily from clinical trials, in patients receiving deferasirox. There have been occasional post-marketing reports of leukocytoclastic vasculitis, urticaria, erythema multiforme, and hypersensitivity reactions (anaphylaxis and angioedema). Detailed information on the safety evaluation of deferasirox is provided in the current [Investigator Brochure]. Mild, non-progressive increases in serum creatinine, mostly within the normal range, occurred in approximately 36% of patients. These were dose-dependent, often resolved spontaneously and some were alleviated by reducing the dose. Rare cases of acute renal failure, mostly serum creatinine increases ≥ 2 x ULN have been reported following the prescription use of deferasirox; these were usually reversible after treatment interruption.

Elevations of liver transaminases were reported as an adverse reaction in approximately 2% of patients. These were not dose dependent and most of these patients had elevated levels prior to receiving deferasirox due to a high background incidence of chronic viral hepatitis and of liver damage secondary to chronic iron overload. Elevations of transaminases > 10 x ULN, suggestive of hepatitis, were uncommon (0.3%). There have been post-marketing reports of hepatic failure, mostly in patients with severe baseline liver disease.

Reports of cytopenias have mostly been in patients with pre-existing blood disorders which are frequently associated with failure of the bone marrow to produce sufficient amounts of blood cells.

As with other iron chelator therapies, high frequency hearing loss and lenticular opacities (early cataracts) have been uncommonly observed in patients treated with deferasirox.

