Mean SF significantly decreased at one year: -121 ng/mL (95% CI: -203, -38) and -222 ng/mL (95% CI: -304, -140) for deferasirox 5 and 10 mg/kg/day groups while there was an increase in the placebo (115 ng/mL: 95% CI: 33, 196); difference vs placebo was significant (-235 ng/mL, $P<0.001$ and -337 ng/mL, $P<0.001$ for deferasirox 5 and 10 mg/kg/day, respectively).

Overall AE rates were 80.4, 76.4 and 78.2% in the placebo, deferasirox 5 and 10 mg/kg/day groups; respectively. The most common investigator-assessed drug-related AEs in the overall placebo (n=56), deferasirox 5 and 10 mg/kg/day groups, respectively, were nausea (7.1, 5.5 and 7.3%), rash (1.8, 3.6 and 9.1%), diarrhea (1.8, 0 and 9.1%), headache (3.6, 3.6 and 1.8%) and upper abdominal pain (0, 3.6 and 1.8%). Serious AEs were reported in 14.3, 12.7 and 16.4% of patients in the placebo, deferasirox 5 and 10 mg/kg/day groups, respectively. Three (5.5%) deferasirox-treated patients (deferasirox 10 mg/kg/day) had 2 consecutive serum creatinine level increases $>33\%$ above baseline and $>$ upper limit of normal (ULN). One patient in the placebo group had an ALT increase >5 x ULN and >2 x baseline and 2 patients had an AST increase to >5 xULN and > 2 x baseline, 1 in the deferasirox 10 mg/kg/day and 1 in the placebo group (Taher 2012).

Therefore, in patients with NTDT and iron overload, deferasirox at starting doses of 5 and 10 mg/kg/day with dose escalation up to 20 mg/kg/day reduced iron overload, as evidenced by significant decreases in LIC and SF and with an overall safety profile comparable to placebo (Ta^her 2012). The reduction in LIC was shown to be dose-dependent since the reduction in LIC by average actual dose showed that patients who received deferasirox $>12.5\text{--}\leq 17.5$ mg/kg/day achieved the greatest LIC decrease, followed by the $\geq 7.5\text{--}\leq 12.5$ mg/kg/day subgroup and the $>0\text{--}<7.5$ mg/kg/day subgroup. Patients who had their dose doubled to 20 mg/kg/day achieved greater reductions in LIC compared with patients who remained on the 10 mg/kg/day starting dose (Ta^her et al. 2013). Continued treatment with deferasirox at appropriate doses for up to 2 years resulted in a progressive reduction in iron overload; mean change -7.14 mg Fe/g dry weight (dw) (mean dose 9.8 ± 3.6 mg/kg/day; Ta^her 2013).

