10.5.10.5 Tolerability

Incidence of grouped gastro-intestinal adverse events (defined by MedDRA terms to be specified in the more detailed RAP document) will be presented as well as Kaplan-Meier curves for time to first occurrence of such AEs.

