2.7.1 Adverse events (AEs)

AEs and the principal cause of death will be coded using MedDRA 20.1.

All summaries of AEs only included treatment emergent AEs, i.e., AEs which started or worsened on or after the day with first study medication intake and not more than 30 days after last study medication.

The incidence of AEs (number and percentage of patients with AEs) will be summarized by MedDRA primary SOC and preferred term, and separately by preferred term only. These two summaries will be generated for all AEs, serious AEs (SAEs), AEs with suspected relationship to study medication, SAEs with suspected relationship to study medication, AEs leading to discontinuation of study medication, and AEs leading to dose adjustment or interruption. AEs will be also summarized by MedDRA primary SOC, preferred term, and maximum severity. Non-serious AEs (i.e. excluding SAEs) will be also summarized by primary SOC and preferred term.

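### SAP 2.7.4.3 pools nausea under the label *Vomiting*, so no planned summary separates the event counts, onset or duration of the two symptoms

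*SAP*

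**What the plan says.** SAP 2.7.4.3 (Tolerability) lists seven groups of gastrointestinal preferred terms. The fifth is "Vomiting (preferred terms of Discoloured vomit, Nausea, Retching, or Vomiting". The other six cover abdominal pain, dyspepsia, diarrhoea, constipation, abdominal distension and oesophagitis. Nausea appears nowhere else in the list.

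Of these groups the SAP says: "These events will be investigated with regards to frequency, time to onset, duration and outcome (event end yes/no". For each patient and group it derives an event count, a time to first event and the length of the first event, and then: "The median time to first event and the median duration of first event will be estimated using Kaplan-Meier methods". It also presents incidence by group.

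The protocol delegates the grouping. Its section 10.5.10.5 says: "Incidence of grouped gastro-intestinal adverse events (defined by MedDRA terms to be specified in the more detailed RAP document) will be presented", and adds Kaplan-Meier curves for time to first occurrence.

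Elsewhere the two symptoms are named separately. Protocol 1.2.1.2 describes the usual gastrointestinal reactions as "mainly nausea, vomiting, diarrhea, or abdominal pain". In its account of the earlier placebo-controlled NTDT study it reports nausea alone: the most common drug-related events "were nausea (7.1, 5.5 and 7.3%), rash (1.8, 3.6 and 9.1%), diarrhea (1.8, 0 and 9.1" per cent on placebo, 5 and 10 mg/kg/day. Vomiting is not in that list.

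SAP 2.7.1 is also relevant. The incidence of adverse events "will be summarized by MedDRA primary SOC and preferred term, and separately by preferred term only".

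**The concern.** The label and the content of the group disagree. A reader of the final report who looks up how many vomiting events patients had, when vomiting began or how long it lasted will find figures that include nausea without vomiting. Nothing in the output title would show this.

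Grouped gastrointestinal tolerability is an analysis that the protocol itself asks for, and counts, onset and duration are what SAP 2.7.4.3 adds to the general adverse event tables. Those added results are the ones that cannot be read as labelled. The report would also carry two patient counts under the word vomiting, one by preferred term and one by group, and they can differ.

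**Working it through.** **1. What follows from the definition alone.** For one patient, let *N* be the day of the first Nausea event and *V* the day of the first event among Vomiting, Discoloured vomit and Retching, with either set to infinity if it never occurs.

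- Group onset is min(*N*, *V*), which is never later than *V*.
- The patient is a group case if *N* or *V* is finite. The number of group cases is therefore at least the number with finite *V*.
- The number of group events is the nausea events plus the others, so it is at least the number of others. Protocol 8.1.1 asks for signs and symptoms to be reported as separate adverse events when no diagnosis is clear, and SAP 2.7.4.3 gives no merging rule. One episode of nausea with vomiting can therefore count twice.
- If *N* < *V*, the duration analysed is that of the nausea. The later vomiting contributes neither onset nor duration. Whether this lengthens or shortens the result cannot be told from the documents.

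The ordering of onset holds patient by patient. I do not extend it to the Kaplan-Meier median, which also depends on censoring.

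**2. What other outputs recover.**

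| Quantity | Nausea and vomiting separable in a planned summary? |
|---|---|
| Patients with at least one event | Yes, SAP 2.7.1 preferred-term tables |
| Number of events per patient | No |
| Time to first event | No |
| Duration of first event | No |

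**3. Can the size be computed?** The only relevant rates are the drug-related nausea rates in protocol 1.2.1.2. They reproduce as whole patients: 4/56 = 7.1% (placebo), 3/55 = 5.5% (5 mg/kg/day) and 4/55 = 7.3% (10 mg/kg/day). The pooled deferasirox count is 7/110. Applied to the 134 enrolled, 134 × 3/55 = 7.3 and 134 × 4/55 = 9.7, or about 7 to 10 patients with drug-related nausea.

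No vomiting count is given, so it must be assumed. With *v* vomiting patients per 110:

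- nausea share of the group, no overlap = 7/(7 + *v*)
- group count relative to vomiting alone = (7 + *v*)/*v* with no overlap, max(7, *v*)/*v* with full overlap

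| Assumed *v* | Nausea share, no overlap | Ratio, no overlap | Ratio, full overlap |
|---|---|---|---|
| 1 | 7/8 = 88% | 8.0 | 7.0 |
| 3 | 7/10 = 70% | 3.3 | 2.3 |
| 7 | 7/14 = 50% | 2.0 | 1.0 |
| 8 | 7/15 = 47% | 1.9 | 1.0 |

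The row *v* = 3 corresponds to vomiting being as rare as the least frequent listed event, "upper abdominal pain (0, 3.6 and 1.8" per cent, or 2/55 + 1/55 in the deferasirox arms. The ratio runs from 1.0 to 8.0 over these assumptions, so the documents fix no figure. These ratios also concern patient counts, which SAP 2.7.1 already separates. For event counts, onset and duration the documents give no data at all.

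**The case against.** The strongest reply is that the SAP does what the protocol told it to do. The protocol calls for grouped events, leaves the terms to the analysis plan, and the SAP discloses every preferred term. Other headings in the list are loose too: *Oesophagitis* takes in oesophageal discomfort and pain, and *Diarrhoea* takes in frequent bowel movements. Incidence by preferred term is tabulated for all, serious, drug-related and discontinuation-related events, among others, and all safety data are listed. The output is descriptive, in a single-arm study, with no test or decision rule attached.

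Most of this stands. There is no breach of the protocol, incidence is recoverable, and individual episodes should be traceable in listings. Where to place Retching is a matter of judgement. If events are as rare as in the earlier study, a median time to first event may not be reached under either definition. None of this makes the label accurate, and a listing is not a summary. Nausea also differs from the other loosely grouped terms, because the protocol names it beside vomiting as a reaction in its own right and reports its rate alone.

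Three stronger readings are tempting and are not supported:

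- *The vomiting results will mostly describe nausea, or overstate vomiting several-fold.* Vomiting's absence from a list of most common events, with no stated cut-off, is not a rate. The earlier figures are investigator-assessed drug-related events over one year in arms started at 5 and 10 mg/kg/day. This analysis covers treatment-emergent events of any cause, over up to five years and at up to 30 mg/kg/day.
- *The true frequency of vomiting is hidden.* SAP 2.7.1 gives it by patient.
- *The pharmacokinetic exclusions are affected.* SAP 2.8 applies its own rule on vomiting near sampling and does not use this group.

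**Conclusion.** The point holds as a grouping and labelling fault confined to SAP 2.7.4.3. As written, patients with nausea only are reported as *Vomiting* cases, and event counts, onset and duration for the two symptoms are mixed with no planned summary that separates them. The direction is certain for the patient and event counts (never lower) and for each patient's onset (never later). It is unknown for duration. The size is not computable without a vomiting rate; the range in the working is conditional on assumed counts and shows only that the answer is open. The primary endpoint, the sample size and the type I error rate are not touched. The fault is modest in consequence and worth correcting because the correction is nearly free.

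**What to change.** In SAP 2.7.4.3, replace the present group with two: *Nausea* (preferred term Nausea) and *Vomiting* (Vomiting, Discoloured vomit, Retching). Report the number of events, time to first event and duration of first event for each. If the pooled group is kept for comparison with earlier reports, label it *Nausea/vomiting*.

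This takes one line of SAP text and adds one row group to existing outputs. It needs no new data, since the preferred terms are already coded.
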